4.3.1 Control of Type I error

The experiment-wise type I error will be controlled to a maximum of 5%. A hierarchical closed testing procedure will be employed such that key secondary endpoints will be considered for statistical significance (in terms of superiority) only if non-inferiority of the primary endpoint is concluded and that a key secondary endpoint will be considered for statistical significance only if the test ordered before it is found to be statistically significant. At each step, dapagliflozin plus saxagliptin added to metformin versus glimepiride added to metformin will be tested first followed by the test for dapagliflozin added to metformin versus glimepiride added to metformin except for the superiority tests of the primary endpoint and the endpoint of total body weight. The test of superiority for HbA1c will include only the comparison of dapagliflozin plus saxagliptin added to metformin versus glimepiride added to metformin. For total body weight, dapagliflozin added to metformin versus glimepiride will

be tested first followed by dapagliflozin plus saxagliptin added to metformin versus glimepiride added to metformin.

The following testing order will be followed for the overall type I error control:

- 1. Change from baseline in HbA1c at Week 52 (test for non-inferiority)
- 2. Proportion of patients reporting at least 1 episode of confirmed hypoglycaemia at Week 52 (test for superiority)
- 3. Change in total body weight from baseline to Week 52 (test for superiority)
- 4. Change from baseline in HbA1c at Week 52 (test for superiority of dapagliflozin plus saxagliptin added to metformin vs glimepiride added to metformin only)
- 5. Change in FPG from baseline to Week 52 (test for superiority)
- 6. Time to rescue at Week 52 (test for superiority)

The statistical comparisons will be done using a comparison-wise type I error of 5% (2-sided). For all other secondary variables and exploratory variables, nominal p-values will be reported without multiplicity controlled significance testing.

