4.5.7 Analysis of proportions

Proportions endpoints will be analysed using logistic regression with the baseline measure as a covariate. The adjusted percentage with 95% CI, Odds Ratio with 95% CI and nominal p-values for the comparison of dapagliflozin or dapagliflozin plus saxagliptin vs glimepiride will be presented. The confidence intervals will be based on the profile likelihood method. When there are less than 5 responders in any treatment group, the unadjusted proportions (and difference), exact 95% confidence interval, and p-values from the Fisher's exact test (when applicable) will be provided.

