4.8 Efficacy analyses

The following table provides a summary of how each efficacy variable will be analysed:

Table 11 Statistical analyses to be conducted and sensitivity analyses

Efficacy Variable	Analyses
Primary:	
Change in HbA1c from baseline to week 52	Primary analysis:
	MMRM (Full Analysis Set)
	Sensitivity analyses:
	MMRM (Per Protocol Analysis Set)
	ANCOVA using values prior to rescue treatment (LOCF used if the week 52 value is not available)
	MMRM primary model repeated including all values regardless of whether patient used rescue treatment or discontinued treatment
	Subgroup analyses:
	MMRM with covariates for each of the following: age group, gender, race, country, baseline HbA1c and baseline eGFR
Key Secondary:	
Proportion with at least one episode of confirmed hypoglycaemia	Logistic regression
Change in body weight from baseline to week 52	MMRM
Change in FPG from baseline to week 52	MMRM
Time to rescue	Cox PH model
Other Secondary:	
Proportion achieving HbA1c <7% (and <7.5%) without confirmed hypoglycaemia at week 52	Logistic regression

Proportion achieving HbA1c <7% (and <7.5%) Logistic regression

at week 52

Proportion achieving individually agreed HbA1c Logistic regression

targets at week 52

Proportion with an HbA1c decrease of ≥1% with Pearson's Chi-square test

no weight gain at week 52

Time spent below HbA1c target (<7% and ANCOVA

<7.5%)

Change in BMI from baseline to week 52 ANCOVA (LOCF)

Proportion with a weight reduction ≥5% or a Logistic regression

weight gain $\geq 5\%$ at week 52

Proportion with at least 1 episode of any

Logistic regression

hypoglycaemia

Change in waist circumference from baseline to ANCOVA (LOCF)

week 52

Change in systolic BP from baseline to week 52 MMRM

Proportion with at least one episode of Logistic regression hypoglycaemia (symptomatic with blood

glucose \leq 70 mg/dL [3.9mmol/L])

Note: Each analysis is based on the Full Analysis Set unless otherwise stated.

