The proportion of patients with at least one episode of confirmed hypoglycaemia, the proportion achieving HbA1c <7% (and <7.5%) without confirmed hypoglycaemia at week 52, the proportion achieving HbA1c <7% (and <7.5%) at week 52, the proportion achieving their individually agreed HbA1c targets at week 52, the proportion with at least one episode of any hypoglycaemia and the proportion with at least one episode of hypoglycaemia (symptomatic with blood glucose ≤70mg/dL [3.9mmol/L]) will be summarised by treatment group and compared between treatment groups using logistic regression with baseline HbA1c as a covariate (see section 4.5.7). The adjusted percentage with 95% CI, Odds Ratio with 95% CI and nominal p-values for the comparison of dapagliflozin or dapagliflozin plus saxagliptin vs glimepiride will be presented. The confidence intervals will be based on the profile likelihood method.

The proportion of patients achieving a \geq 5% weight reduction or \geq 5% weight gain will be summarised by treatment group and compared between treatment groups using logistic regression with baseline weight as a covariate.

The proportion of patients with an HbA1c decrease ≥1% with no weight gain at week 52 will be summarised by treatment group and comparisons between treatment groups (contrasts of each test combination vs the control) will be performed using a Pearson's Chi-Square test. Nominal p-values and asymptotic 95% CIs will be presented.

Descriptive summaries of change from baseline in HbA1c, FPG, weight, BMI, waist circumference and systolic BP over time (observed values), will be presented in addition to the analyses described above.

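### One responder endpoint, an HbA1c fall of at least 1 point without weight gain, is tested by unadjusted chi-square, an unexplained exception to the SAP's baseline-adjusted rule for proportions (minor)

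*SAP*

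**What the plan says.** Section 4.5.7 gives the general rule: "Proportions endpoints will be analysed using logistic regression with the baseline measure as a covariate". Its only alternative, an exact test, is for sparse data: "When there are less than 5 responders in any treatment group, the unadjusted proportions (and difference), exact 95% confidence interval, and p-values from the Fisher's" (the quotation stops at the name of that test).

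Section 4.8.2 follows this rule for the HbA1c-target and hypoglycaemia proportions, which are "compared between treatment groups using logistic regression with baseline HbA1c as a covariate (see section 4.5.7"). The proportions with a 5% weight change are "compared between treatment groups using logistic regression with baseline weight as a covariate".

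For an HbA1c decrease of at least 1% without weight gain, section 4.8.2 instead says that "comparisons between treatment groups (contrasts of each test combination vs the control) will be performed using a Pearson's Chi-Square test", and adds: "Nominal p-values and asymptotic 95% CIs will be presented". The Table 11 row, with its two columns run together in the text, says the same: "Proportion with an HbA1c decrease of ≥1% with Pearson's Chi-square test".

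Section 4.3.1 fixes the endpoint's status: "For all other secondary variables and exploratory variables, nominal p-values will be reported without multiplicity controlled significance testing".

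**The concern.** The plan adjusts hypoglycaemia proportions for baseline HbA1c, yet leaves unadjusted a responder endpoint whose HbA1c component is itself a change from baseline. Entry HbA1c runs from 7.5% to 10.5% (Appendix II), so a 1-point fall means reaching 6.5% or below at one end and 9.5% or below at the other. Baseline HbA1c is therefore a natural prognostic covariate, and the primary model in 4.5.4 already uses it.

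Three things are at stake, all modest:

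- A chance difference in baseline HbA1c between arms is left in the comparison.
- Some precision may be lost.
- The result is not on the same scale as the adjusted percentages and odds ratios of the related endpoints. Section 4.8.2 also does not say which quantity the asymptotic interval estimates.

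**Working it through.** **Passages side by side.** Table 11 has eight rows for proportion endpoints. Seven are assigned logistic regression and one Pearson's chi-square. Section 4.5.7 announces no exception apart from the sparse-data fallback. Section 5 lists only the reversed direction of the primary hypotheses. The two places that name this endpoint, 4.8.2 and Table 11, agree with each other.

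**The plan's own figure.** The SAP gives no response rate, power or sample size for this endpoint. Its only power statement concerns the primary test (section 1.3): margin 0.30, SD 1.0, true difference 0, one-sided 0.025, about 95% power.

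- n per arm = 2 × (1.960 + 1.645)² × 1.0² / 0.30² = 288.8, rounded up to 289, against 290 stated.
- Power at 290 per arm is 95.1%.

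The figure reproduces. It serves here only to supply n = 290 per arm.

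**Power, chi-square against baseline-adjusted logistic regression.** All response inputs are assumptions:

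- baseline HbA1c normal, mean 8.3 and SD 0.75, truncated to 7.5–10.5;
- SD of change 1.0;
- probability of no weight gain 60–95%;
- week-52 data present in 85–95% of patients;
- size of the baseline-to-change correlation 0 to 0.6;
- missing data count as failure (section 4.6.2).

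To mimic rescue, half the scenarios also count patients above HbA1c 8.0% as failures. Each scenario had 2500 to 3000 simulated trials at two-sided 0.05, and the adjusted test was the likelihood-ratio test with baseline HbA1c as covariate. The rows below assume no arm difference in mean HbA1c change, no weight gain in 95% against 70%, and week-52 data in 95%.

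| Rescue mimicked | Correlation | Responders, test / control | Chi-square | Adjusted |
|---|---|---|---|---|
| no | 0.3 | 41.3% / 30.4% | 78.7% | 79.8% |
| no | 0.5 | 41.0% / 30.2% | 76.7% | 82.0% |
| no | 0.6 | 40.5% / 29.9% | 77.3% | 84.7% |
| yes | 0.3 | 38.5% / 28.3% | 74.2% | 74.7% |
| yes | 0.5 | 38.1% / 28.1% | 72.2% | 74.7% |
| yes | 0.6 | 38.2% / 28.1% | 74.0% | 78.3% |

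With 3000 trials, a power near 75% has a simulation standard error of √(0.75 × 0.25 / 3000) = 0.8 points, so gains of about one point or less should be read as none.

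Over all scenarios the gain was about 0 at correlation 0, 0–1 point at 0.3, 1–5 at 0.5 and 1–7 at 0.6. It was at most about 5 points with rescue mimicked. A separate simulation, also under assumed inputs, gave 0–7 points, falling to 0–2 when week-52 HbA1c above 8.0% counted as non-response. In it, adding baseline weight as a second covariate cost no power. Type I error was 0.046–0.058 over the null scenarios for both tests.

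**Chance imbalance.** With an assumed baseline SD of 0.62, the 1.96-SE limit for the difference in mean baseline HbA1c is 1.96 × 0.62 × √(2/290) = 0.10. The further assumptions are a mean change of −0.9 at baseline 8.5, 60% without weight gain and 85% observed. A difference of 0.10 then moves the responder proportion by 1.0, 1.7 and 2.0 percentage points at correlations 0.3, 0.5 and 0.6. The standard error of the responder difference is about 3.5 points.

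**The case against.** The strongest reply is that nothing here is ambiguous or invalid. Section 4.5.7 is a general definition. The endpoint-specific text and Table 11 both name chi-square, so an analyst knows what to run. The test holds its size, no power is claimed for this endpoint, and its p-value is nominal. The unadjusted interval already reflects the play of chance in baseline. Section 4.5.7 speaks of a single baseline measure, whereas this composite has two, so it cannot be applied as written. Adjustment also changes the effect measure to a covariate-conditional odds ratio.

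Most of this stands and sets the severity. It does not explain why one endpoint of a family is treated differently. The two-covariate difficulty is met by naming both.

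A reader might infer more than the document supports:

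- **That the chi-square result would be wrong.** It would not; type I error is about 5% with either test.
- **That power is certainly lost.** The loss depends on a baseline-response relation that the SAP does not state, and it vanishes if that relation is weak.
- **That this endpoint would gain most from adjustment.** Rescued patients count as failures (4.6.2), and the rescue criterion for weeks 24 to 52 is HbA1c above 8.0%. A patient starting above 9.0% can thus fall by 1 point and still meet it. Assume a slope of change on baseline of −0.5, a mean change of −0.9, an SD of change of 1.0 and 70% without weight gain. Counting values above 8.0% as failures then cuts the baseline-response correlation from 0.18 to 0.09, against −0.21 for HbA1c below 7%. At slope −0.9 the order reverses.

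**Conclusion.** The point holds as a minor one. The SAP makes an undeclared and unexplained exception to its own rule for proportions, on an endpoint where a baseline covariate is plainly relevant.

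The cost is uncorrected chance imbalance, worth about 1 to 2 percentage points at the 1.96-SE limit against a standard error of about 3.5, and a possible precision loss of about 0 to 7 power points, in most scenarios 0 to 3. These sizes rest wholly on assumed response rates, correlations and rescue effects. The inconsistency itself can be read directly from the document. No confirmatory conclusion is affected.

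**What to change.** In section 4.8.2 and Table 11, replace the chi-square test for this endpoint with the 4.5.7 logistic regression, and name baseline HbA1c and baseline weight as the covariates. Report adjusted percentages and odds ratios with profile-likelihood intervals, and state that the Fisher fallback for fewer than 5 responders in a group applies. Because the odds ratio is conditional on the covariates, also show the unadjusted proportions and their difference.

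The cost is a short text change, made before unblinding. Both covariates are already collected and the method is already specified. If the sponsor prefers chi-square, the lesser repair is to declare the exception in 4.5.7 with its reason and to say what the asymptotic interval estimates.

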4.8.3 Exploratory Variables

The summaries described below will be based on the Full Analysis Set including values prior to rescue treatment or discontinuation. Values recorded after rescue treatment for those patients who used rescue medication or values collected more than 8 days after last dose date for patients who stayed more than 8 consecutive days off treatment are excluded from the analyses.

4.8.3.1 SF-36v2

The SF-36v2 questionnaire contains 36 items and covers 8 health domain scales and 2 psychometrically based physical and mental component summary measures. The 8 health domain scales are referred to as follows: physical functioning (PF); role - physical (RP); bodily pain (BP); general health (GH); vitality (VT); social functioning (SF); role - emotional (RE); mental health (MH). The 2 summary measures are referred to as the physical component score (PCS) and mental component score (MCS).

Standardised scores will be generated using the validated scoring software package (QualityMetric Health OutcomesTM Scoring Software 4.5 (or later version)) for the 8 health domain scales and 2 summary measures using the raw data entered in the eCRFs.

The scores for each of the 8 health domain scales along with the PCS and MCS summary measures will be summarised by absolute values and changes from baseline at week 24 and week 52.

4.8.3.2 HFS II – Worry subscale

A mean summary score will be calculated by summing the responses to the 18 questions and dividing by the number of answered questions. If < 50% of the questions are answered, the mean score will not be calculated. Absolute values and changes from baseline in this mean score will be summarised by treatment group at week 24 and week 52.

4.8.3.3 IWQOL-Lite

A score for each of the 5 domains (physical function, self-esteem, sexual-life, public distress and work) and a total score will be calculated as detailed in Appendix V. The raw scores will be converted to transformed scores (ranging from 0 to 100) as described in Appendix V. Absolute values and change from baseline in the transformed scores will be summarised by treatment group at week 24 and week 52.

4.8.3.4 Waist:Hip ratio

Change from baseline in waist:hip ratio will be summarised at week 52.

4.8.4 Sensitivity analysis

To assess the robustness of the primary efficacy results, sensitivity analyses will be carried out as follows for change from baseline in HbA1c to week 52:

- The primary MMRM model will be repeated using the Per-Protocol analysis set
- An ANCOVA analysis will be performed using values prior to rescue treatment at
 week 52. If the Week 52 value is missing or post rescue treatment/discontinuation, the
 last post-baseline measurement prior to week 52 and prior to rescue treatment will be
 used.
- The primary MMRM model will be repeated including all values according to the ITT principle (i.e. all values will be included regardless of use of rescue treatment or treatment discontinuation)

In addition, as noted in section 4.6.2, summaries of missing data by visit will be used to assess the missing data assumptions (See example in Table 16 in Appendix IV). A spaghetti plot to show drop-out patterns over time will also be provided.

4.8.5 Subgroup analyses

The primary efficacy analysis will be repeated to summarize HbA1c within subgroups based on: age group ($<65, \ge 65 - <75, \ge 75$ yrs), gender, female age group ($\le 50, >50$ yrs), race, country, baseline HbA1c ($<8\%, \ge 8\% - <9\%, \ge 9\%$), and baseline eGFR ($<30, \ge 30 - <45, \ge 45 - <60, \ge 60 - <90, \ge 90$ mL/min/1.73m²). The primary MMRM model will be repeated as described in Section 4.5.4.3. The nominal p-value for the subgroup-by-treatment interaction at week 52 will be presented.

If the value of the grouping variable cannot be determined, the patient will be excluded from the corresponding subgroup analysis. For each subgroup analysis, if, in any treatment group, the number of patients is less than 10 for a subgroup, this subgroup will not be included in the interaction model and descriptive summaries only will be displayed. If there are problems with the convergence of the MMRM model, descriptive summaries within subgroups will be provided.

4.9 Safety analysis

All safety analyses will be performed on the Safety Analysis Set. Summaries of safety data will be produced for the double-blind (DB) treatment period (on-treatment) only, while listings will include all events, i.e., listings will include values during the pre-treatment period, during the DB treatment period and during the follow-up period.

A separate page to capture events of hypoglycaemia is contained within the CRF (AZ module HYPOE). Hypoglycaemia (or discontinuation due to hypoglycaemia) will not be reported on an AE CRF page unless the event fulfilled criteria for SAE (in which case a SAE form will be completed). Hypoglycaemia events that are reported as SAEs will be included in all

summaries of AEs or SAEs. Separate summaries will be provided including hypoglycaemia events reported on that special CRF page (see Section 4.9.6).

Analysis of changes from baseline to a specific time point (e.g., laboratory parameters and vital signs) will only include patients from the Safety Analysis set who have data available for both the baseline and the time point under consideration unless otherwise specified.

SAEs and the lab measurements for the liver function tests will be included in the summaries only if they occurred or were measured on or prior to the 30th day after the last blinded drug treatment date. All other safety events (non-severe AEs, hypoglycaemia, etc.) and measurements (safety labs, vital signs etc.) will be included in the summaries only if they occurred or were measured on or prior to the 4th day after the last blinded drug treatment date.

No formal statistical testing will be performed for safety analyses; only descriptive summaries will be provided. A dot plot (showing relative risk) will be produced for the most common adverse events.

4.9.1 Adverse events

Adverse events will be classified by Primary System Organ Class (SOC) and Preferred Term (PT) according to the MedDRA (version 19.1 or later). Summaries of AEs will be produced by SOC, PT and treatment group. In summaries by SOC and PT, AEs will be sorted by decreasing frequency within each SOC and PT according to the dapagliflozin + metformin dose group. In summaries by PT, AEs will be sorted by decreasing frequency within PT according to the dapagliflozin + metformin dose group.

Summaries of AEs will report the number (and percentage of patients) of the following:

- All AEs (including AEs, SAEs, death, hypoglycaemia, treatment-related events and events leading to the discontinuation of study medication)
 - a) using data obtained prior to rescue medication only
 - b) repeated to contain all data regardless of use of rescue medication
- AEs by SOC and PT
 - a) using data obtained prior to rescue medication only
 - b) using all data regardless of use of rescue medication

The following summaries will be provided using all data regardless of use of rescue medication:

- AEs by SOC and PT by age categories
- AEs by SOC and PT by gender
- AEs by SOC and PT by female age categories
- AEs by SOC and PT by race
- Most common AEs (i.e., occurring in at least 2% of patients in any treatment group) by PT
- AEs by SOC, PT and intensity

- Treatment-related AEs by SOC and PT
- Most common AEs (i.e., occurring in at least 5% of patients in any treatment group) by PT

AEs will be summarised for the double-blind treatment period only; listings of AEs will include all events throughout the study period (i.e. pre-treatment period, double-blind treatment period and follow-up).

A dot plot (showing relative risk) will be produced for the most common adverse events (by preferred term).

4.9.2 Serious adverse events

All serious adverse events (SAEs) will be described in narratives, regardless of investigator assessment of causality.

Summaries of SAEs will be produced for the double-blind treatment period (using all data regardless of use of rescue medication) and will consist of:

- SAEs by SOC and PT
- SAEs related to study medication by SOC and PT

Listings of SAEs will include all events throughout the study period i.e. pre-treatment period, double-blind treatment period and follow-up.

4.9.3 Adverse events leading to discontinuation of study medication

AEs with an onset during the double-blind treatment period reported with an action taken of permanent discontinuation of study medication will be summarised by SOC and PT (using all data regardless of use of rescue medication). This summary will include hypoglycaemia events that were reported as SAEs.

In addition to a narrative description, a patient listing of discontinuation due to AEs will be provided - displaying all events that led to discontinuation of study medication with an onset date prior to the double-blind treatment period and up to the follow-up period, if any.

4.9.4 Adverse events of special interest

Adverse events of special interest (AEOSI) will be defined based on lists of preferred terms. These lists will be reviewed and finalized prior to database lock and unblinding of the database.

The following summaries and listings of AEOSI will include all data regardless of use of rescue medication:

- AEs of genital infection
- AEs of genital infection by gender

- AE of antimicrobial treatment for genital infection by gender
- AEs of Urinary Tract Infection (UTI)
- AEs of UTI by gender
- AEs of antimicrobial treatment for UTI by gender
- AEs of renal impairment/failure
- AEs of volume depletion
- AEs of fracture
- AEs of hepatic disorder
- AEs of hypersensitivity reactions
- AEs of severe cutaneous adverse reactions
- AEs of gastroenteritis and upper respiratory tract infections
- AEs of decreased lymphocyte count
- AEs of pancreatitis
- AEs of all malignancies
- AEs of confirmed adjudicated hospitalisations for cardiac failure events
- AEs of cardiac failure
- AEs of DKA

Details of the summaries to be provided for events of Hypoglycaemia can be found in Section 4.9.6.

